# 4.1 **REGISTRATION AND RUN-IN PERIOD**

Participants that meet all the inclusion criteria and none of the exclusion criteria for their cohort and wish to participate, should sign the Add-Aspirin Consent Form. These participants will then be registered via the trial website and assigned a participant identification number.

All participants will be required to complete an active run-in period after registration but prior to randomisation where they will take 100mg aspirin daily (one tablet per day) open-label, for a period of approximately 8 weeks. At the end of this run-in period, the participant's tolerance of aspirin and adherence to daily treatment will be assessed (see section 6.2). Those participants identified as suitable for further study participation, and who remain eligible and are willing to continue in the trial should then re-confirm their consent to participate (see section 3.10) before being randomised.

For those who do not go on to be randomised, active participation in the trial will end at this time and no further CRFs are required after the end of run-in assessment. However, passive follow-up will continue via routinely-collected healthcare datasets, if the participant has given consent for this (see section 9.3.1). This approach will allow those individuals who are unlikely to be able to tolerate aspirin, as well as those who are unlikely to be able to adhere to the protocol treatment schedule, to be identified. See section 5.1 and section 6.2 for further details on the run-in period treatment and assessments at the end of the run-in period.

# 4.2 TIMING OF INITIATION OF THE RUN-IN PERIOD WITHIN THE CANCER TREATMENT PATHWAY

The following section describes when the active run-in period can be started relative to the treatment pathway. Potential participants can be given information about the trial before this time. If the potential participant has received treatment as part of another trial, please see section 4.4.

Examples of likely clinical scenarios are given below. For other clinical scenarios, or cases where potential participants fall outside of the timing of entry criteria, and there is a valid reason, please discuss with the MRC CTU at UCL where eligibility will be considered on a case by case basis. In all cases, timing of entry into the run-in period is calculated from the most recent curative treatment received.

# 4.2.1 BREAST COHORT

For these participants, hormone therapy and/or trastuzumab may be planned or ongoing. A diagram of the timing of entry criteria for the breast cohort is available in appendix VIII.

- a) **Surgery and no adjuvant chemotherapy or radiotherapy planned:** the run-in period can start between 6 and 12 weeks after definitive surgery (defined as wide local excision or mastectomy).
- b) **Surgery and adjuvant chemotherapy (no radiotherapy planned):** the run-in period should start after chemotherapy has ended (e.g. day 21 of a 3 week cycle) and no later than 6 weeks after the end of chemotherapy.
- c) **Surgery and adjuvant radiotherapy (no chemotherapy planned):** the run-in period can start 6 weeks after surgery (radiotherapy may be ongoing) and no later than 6 weeks after the last fraction of radiotherapy.
- d) **Surgery and adjuvant chemotherapy followed by adjuvant radiotherapy:** the run-in period should not be started until the chemotherapy has ended (e.g. day 21 of a 3 week cycle) and no later than 6 weeks after the final fraction of radiotherapy.

# 4.2.2 COLORECTAL COHORT

A diagram of the timing of entry criteria for the colorectal cohort is available in appendix IX.

- a) **Surgery and no adjuvant chemotherapy or radiotherapy planned** (but may have been preceded by chemotherapy or radiotherapy): the run-in period should start between 6 and 12 weeks after definitive surgery. **India only:** the run-in period should start between 2 and 12 weeks after definitive surgery.
- b) Surgery and adjuvant chemotherapy (no radiotherapy planned): the run-in period can start after 6 weeks of ongoing chemotherapy providing that the platelet count on day 1 of each of the preceding chemotherapy cycles is ≥100 x 10^9/L. The run-in period should start no later than 6 weeks after the end of chemotherapy including when chemotherapy has been discontinued early (e.g. day 14 of a 2 week cycle or day 21 of a 3 week cycle). There is no minimal amount of chemotherapy.
- c) **Surgery and adjuvant radiotherapy (no chemotherapy planned):** the run-in period can start 6 weeks after surgery (radiotherapy may be ongoing) and no later than 6 weeks after the last fraction of radiotherapy.
- d) **Surgery and adjuvant chemotherapy followed by adjuvant radiotherapy:** the run-in period can start after 6 weeks of chemotherapy providing platelet counts as defined in (b) above. The run-in period should start no later than 6 weeks after the last fraction of radiotherapy.
- e) **\*Surgery and entry into POLEM trial if randomised to adjuvant chemotherapy and Avelumab** (24 week treatment): the run-in period can start after completion of Avelumab and no later than 6 weeks after the end of avelumab.

f) \*Surgery and entry into POLEM trial – if randomised to adjuvant chemotherapy alone (control arm): the run-in period can start after completion of chemotherapy and no later than 6 weeks after the end of chemotherapy.

\*See Appendix XIV for further details regarding Add-Aspirin – POLEM Colorectal Collaboration in selected centres.

### 4.2.3 GASTRO-OESOPHAGEAL COHORT

A diagram of the timing of entry criteria for the gastro-oesophageal cohort is available in appendix X.

- a) Surgery and no adjuvant chemotherapy or radiotherapy planned (but may have been preceded by chemotherapy): In the UK and Republic of Ireland, the run-in period should start between 6 and 16 weeks after definitive surgery. India only: the run-in period should start between 2 and 16 weeks after definitive surgery.
- b) Surgery and adjuvant chemotherapy: the run-in period can start after 6 weeks of ongoing chemotherapy providing that the platelet count on day 1 of each of the preceding chemotherapy cycles is  $\geq 100 \times 10^9$ /L. The run-in period should start no later than 8 weeks after the end of chemotherapy (day 21 of a 3 week cycle) including when chemotherapy has been discontinued early. There is no minimal amount of chemotherapy.
- c) **Surgery and adjuvant chemoradiotherapy:** the run-in period can start after 6 weeks of chemoradiotherapy providing platelet counts as defined in (b) above. The run-in period should start no later than 14 weeks after the last fraction of radiotherapy.
- d) **Definitive chemoradiation:** the run-in period can start as soon as this is complete and no later than 14 weeks after the final fraction of radiotherapy. Where a post-treatment endoscopy is routinely performed at 12 weeks after chemoradiotherapy, the run-in period can start once this has been undertaken and up to four weeks after.
- e) Definitive chemoradiation followed by salvage surgery: In the UK and Republic of Ireland, the run-in period should start between 6 and 16 weeks after definitive surgery. India only: the run-in period should start between 2 and 16 weeks after definitive surgery.

# 4.2.4 PROSTATE COHORT

For these participants, hormone therapy may be planned or ongoing (for a maximum duration of 3 years). A diagram of the timing of entry criteria for the prostate cohort is available in appendix XI.

- a) **Prostatectomy and no adjuvant chemotherapy or radiotherapy planned:** the run-in period should start between 6 and 12 weeks after definitive surgery, providing PSA remains ≤0.1 ng/ml at point of entry. **India only:** the run-in period should start between 2 and 12 weeks after definitive surgery and where registration is before 6 weeks PSA ≤0.1ng/ml should be confirmed at the time of randomisation.
- b) **Prostatectomy and adjuvant radiotherapy:** the run-in period should start at least 6 weeks after surgery and no later than 6 weeks after the last fraction of radiotherapy.

- c) **Radical radiotherapy:** the run-in period can start as soon as this is complete and no later than 12 weeks after the final fraction of radiotherapy.
- d) Salvage radiotherapy following previous prostatectomy (irrespective of previous therapy): the run-in period should start no later than 12 weeks after the final fraction of radiotherapy.

# 4.2.5 **TOXICITY DURING ADJUVANT THERAPY**

Where the run-in period is started while adjuvant chemotherapy and/or radiotherapy is ongoing, and poor tolerance is attributed to the ongoing adjuvant therapy, a further run-in period can be performed when adjuvant therapy is finished, providing that the further run-in commences no later than 8 weeks from day 1 of the last cycle of chemotherapy or from the final fraction of radiotherapy.

# 4.3 RANDOMISATION PROCESS

Participants may be randomised if they meet all of the inclusion criteria and none of the exclusion criteria for their cohort, and are felt to be suitable for long-term treatment with daily aspirin following the run-in period (see section 5.1). The majority of participants (those <75 years) will be randomised (1:1:1) to either 100mg aspirin, 300mg aspirin, or matching placebo. Participants will have an equal chance of receiving 100mg aspirin, 300mg aspirin or a placebo. Participants ≥75 years will be randomised (2:1) between 100mg aspirin and matching placebo only. In all cases, neither the participant nor the investigator will be notified of the final treatment allocation (double-blind).

Further details of the methods used for treatment allocation can be found in section 10.1.

If there are any problems for centres accessing the system, the Trial Managers at the MRC CTU at UCL should be contacted (see page v).

# 4.4 CO-ENROLMENT GUIDELINES

Since aspirin is intended to be given following or alongside standard primary therapy, rather than replacing any element of current treatment, it will be appropriate to include participants who have already taken part in trials of primary treatments wherever possible. This will allow assessment of the efficacy of aspirin in participants who have received both current and potentially future standard treatment.

Participants in a number of specified trials may enter Add-Aspirin (providing they satisfy all other eligibility criteria). This has been agreed with the relevant trial teams. For the most up-to-date list, check www.addaspirintrial.org. If they have participated in another trial that is not listed on the approved list, please contact the MRC CTU at UCL to discuss this prior to their registration into Add-Aspirin. Following registration, participation in another trial should be reported on the Co-enrolment CRF. Note that participation in a previous observational study (where the patient has received treatment as per standard of care) does not require prior approval or reporting on CRFs.

Following entry into Add-Aspirin, if participants should wish to enter subsequent cancer treatment trials (particularly where this is prior to an Add-Aspirin primary outcome event), please contact the Trial Manager to discuss this.

If you have any queries regarding co-enrolment, please contact the MRC CTU at UCL.

# 5 TREATMENT OF PARTICIPANTS

# 5.1 TREATMENT DURING THE RUN-IN PERIOD

See section 4.2 for when the run-in period can commence. All participants will take 100mg aspirin (open-label) once daily for approximately 8 weeks (7-9 weeks is acceptable) prior to randomisation in order to identify those individuals who are unlikely to be able to tolerate aspirin and those who are unlikely to be able to adhere to the protocol treatment regimen. The guidance on investigating and managing treatment toxicity, provided in the subsequent sections, should be followed during the active run-in period as well as during randomised treatment in the trial. Dose reductions will not be relevant during the run-in period and so treatment should be discontinued in the event of significant toxicity.

At the end of the run-in period, treatment adherence and toxicities will be assessed, as described in section 6.2, to identify those participants who are suitable to be randomised into the trial. Participants that experience any aspirin-related severe toxicity (defined as  $\geq$ grade 3 Common Terminology Criteria for Adverse Events (CTCAE v4)) or significant gastrointestinal bleeding (grade 3 and 4), active gastrointestinal ulceration, new cases or worsening tinnitus (grade 2 or above), , intracranial bleeding or hypersensitivity to aspirin should permanently discontinue aspirin immediately and will not be eligible for the trial.

As described in section 6.2, if the Investigator feels that the reason for inadequate adherence is temporary, the run-in period may be extended by 4 or 8 weeks to reassess adherence and toxicity. All extensions to the run-in period must be discussed with the Trial Manager and the trial medication will be resupplied accordingly.

No 'wash-out' period will be necessary between the run-in period and randomisation and the blinded medication should be commenced as close to the end of the run-in period as possible.

# 5.2 RANDOMISED TRIAL TREATMENT

Participants will self-administer one enteric-coated tablet of either 300mg aspirin, 100mg aspirin or matching placebo. This should be taken daily and swallowed whole with plenty of liquid (e.g. a glass of water) preferably after a meal, and at a similar time each day. This should be continued for at least five years or until one of the primary outcome measures is met (see section 10.2). The risk of toxicity with aspirin increases with age and in order to reduce this risk those 75 years old or over will automatically only be randomised to aspirin 100mg or matching placebo. Additionally, prescription of a proton pump inhibitor (PPI) throughout the treatment period is recommended for these patients.

Participants and Investigators will be blinded to treatment allocation. Patient reported adherence to trial treatment will be collected during follow-up.

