Interventions to be compared	Participants will be randomly assigned to 100mg aspirin, 300mg aspirin or matched placebo (see figure $1 - page x$ ). All tablets will be enteric-coated, to be taken daily for at least five years. All participants will take open label 100mg aspirin daily for a run-in period of approximately 8 weeks prior to randomisation.
Co-primary outcome measures	All participants: overall survival Breast cancer: invasive disease-free survival Colorectal cancer: disease-free survival Gastro-oesophageal cancer: overall survival Prostate cancer: biochemical recurrence-free survival
Secondary outcome measures	In all participants these will include adherence, toxicity including serious haemorrhage, and cardiovascular events, as well as some tumour site-specific secondary outcome measures.
Registration and randomisation	Participants can be registered online for the run-in period through the trial website (www.addaspirintrial.org). Following assessment at the end of the run-in period, eligible participants in the UK can be randomised by phone ([name]). Eligible participants in India or Republic of Ireland can be randomised via the trial website. See section 4 for further details of this process. Participants will undergo a double-blind randomisation and will be allocated in a 1:1:1 ratio to either 100mg aspirin, 300mg aspirin or a matched placebo. The randomisation will use minimisation with a random element, balancing for key prognostic factors. Participants who are 75 years old or over, will only be allocated to either 100mg aspirin or
Fatimated Number of	matched placebo.
Estimated Number of participants to be randomised (UK,India and Republic of Ireland)	Total: 9920 participants Breast: 3100 participants Colorectal: 2600 participants Gastro-oesophageal: 2100 participants Prostate: 2120 participants

SUMMARY INFORMATION TYPE	SUMMARY DETAILS
Duration	Participants will be recruited over 3 to 6 years depending on tumour site and will self-administer tablets daily for at least 5 years.

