# 5.7 PROTOCOL TREATMENT DISCONTINUATION

In giving consent to participate in the trial, participants are giving consent to have trial treatment, trial follow-up and data collection. However, an individual participant may stop treatment early for any of the following reasons:

- Unacceptable toxicity or adverse event
- Intercurrent illness that prevents further treatment
- Any change in the participant's condition that justifies the discontinuation of treatment in the Investigator's opinion. This might include prescription of aspirin or another medication that the Investigator feels could not safely be given alongside the trial treatment.
- Inadequate compliance with the protocol treatment in the judgement of the Investigator (compliance should be discussed and documented at each follow-up visit as indicated in the assessment schedule)
- Pregnancy
- Early cessation of trial treatment by the participant

As participation in the trial is entirely voluntary, a participant may choose to discontinue the trial treatment at any time without giving any reason, and without their medical care or legal rights being affected. Although the participant is not required to give a reason for discontinuing their trial treatment, any reasons given will be documented on the Early Cessation of Trial Treatment CRF (Form 12).

Participants should remain in the trial for the purpose of follow-up and data analysis unless they additionally wish to withdraw their consent for this. If a participant wishes to withdraw from trial follow-up, refer to section 6.9.

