# 5.8 TREATMENT FOLLOWING DISEASE RECURRENCE/PROGRESSION

When disease recurrence has occurred in patients during the randomised phase of the study, participants should normally continue to take their allocated trial treatment. Where the Investigator feels that this is not appropriate (for example, if the participant will be receiving another treatment that cannot safely be given alongside the trial medication), this should be managed and documented as with any other treatment discontinuation (see section 5.7) and the participant should continue to be followed up in the trial wherever possible. See also section 5.11.4 for guidance on managing participants that require non-trial medication. A temporary discontinuation of trial medication could be considered. Unblinding should not normally be required. It is preferable to assume that the participant is taking an active product (300mg aspirin) and discontinue trial medication (either temporarily or permanently) if necessary. Individual cases can be discussed with the MRC CTU at UCL.

If a disease recurrence event happens during the run-in phase, the participant will not be eligible for randomisation and should not be followed up in the trial.

Note that disease recurrence is an important outcome event in all four tumour site-specific cohorts and should be assessed according to protocol definitions (see section 10.2) and documented on the appropriate CRF(s).

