# 6.3 PROCEDURES FOR ASSESSING EFFICACY

Clinical outcome events, as defined in the Statistical Analysis Plan, will be reported on CRFs to be completed by the Investigator or Research Nurse at each follow-up assessment. Disease recurrence and progression will be assessed at follow-up clinic visits by means of imaging, clinical examination and tumour markers (e.g. carcinoembryonic antigen (CEA), prostate-specific antigen (PSA)) in accordance with routine investigations for that tumour site (see Trial Assessment Schedule). In the prostate cohort, biochemical failure is a primary outcome event and should be reported in accordance with the definitions provided in 6.3.1.

Following disease recurrence/progression in the randomisation phase, participants should normally continue to take their trial medication (see section 5.8 for guidance on treatment following

relapse/progression). Providing they are willing, they should continue to be followed up in the trial, regardless of whether they are still receiving trial medication. Follow-up should adhere as far as possible to the planned assessment schedule, but some variation is acceptable where this differs from local protocols for follow-up after relapse.

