#### **10.2.1 PRIMARY OUTCOME MEASURES**

For the combined cohort analysis, the primary outcome measure will be time to death from any cause. The cohort specific primary outcome measures are also all time-to-event variables and are defined in table7. Details of outcome assessments are given in section 6.

Соногт	PRIMARY OUTCOME MEASURE	
Cohorts combined	Overall survival (OS)	
	Time from randomisation to death from any cause	
Breast cancer	Invasive disease-free survival (IDFS)	
	Time from randomisation to invasive disease or death from any	
	cause. Invasive disease is defined as:	
	Ipsilateral invasive breast tumour recurrence	
	Regional invasive breast cancer (ipsilateral breast)	
	Distant recurrence	
	Contralateral invasive breast cancer	
	
 
Second primary (non-breast) invasive cancer
 
	
Colorectal cancer	Disease-free survival (DFS)	
	Time from randomisation to disease recurrence (local or distant) or	
	death from any cause.	
Gastro-oesophageal cancer	Overall survival	
	Time from randomisation death from any cause.	
Prostate cancer	Biochemical recurrence-free survival (bRFS)	
	Time from randomisation to PSA failure (as defined in 6.3.1),	
	clinical progression, initiation of salvage treatment or prostate	
	cancer death.	

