#### 6A) Assessments and follow-up after disease relapse

If documented tumour recurrence occurs during follow-up no additional visits are required.

Research blood samples will be collected. Furthermore, if the recurrent tumour is amenable to sampling, a research biopsy will be considered in selected centres if appropriate consent had been taken for this additional procedure at baseline. This biopsy could be under radiological (either US or CT scan) or endoscopic guidance (see the laboratory manual for more details). Subjects will need to have pre-biopsy blood tests including haematology, biochemistry and coagulation as indicated in the Assessment Schedule above (Appendix XIV, Section 5).

If a tumour biopsy is required, sites should discuss the recommended duration with which to withhold Add-Aspirin trial medication with the interventional radiologist or endoscopist. Subjects

not on Add-Aspirin, and on POLEM follow up alone, are permitted use of anticoagulants. Generally it is recommended to stop use of antocoagulation 24-48 hours prior to the biopsy and recommencing 24-48 hours after the procedure on recommendation of the interventional radiologist or endoscopist. Subjects who are on oral coumadin derivatives (i.e., warfarin) will be strongly encouraged to switch to subcutaneous anticoagulants (i.e., low molecular weight heparin) at study entry. However, if this is not possible due to clinical reasons or subject preference, the coagulation parameters will be carefully monitored by the treating physician and the interventional radiologist or endoscopist performing the procedure.

Any other POLEM study-related procedure should be discontinued upon tumour recurrence and subjects will be treated and followed up as per standard of care. Nevertheless, the following information should be still collected for all subjects:

- Details of any post-recurrence therapies should be recorded.
- Follow up for survival should continue every 6 months until death or trial closure. This may occur by telephone contact or via the patient's general practitioner

Participants on the Add-Aspirin trial can continue trial medication upon recurrence, as per Section 5.8 of the main Add-Aspirin Protocol.

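### Protocol section 5.2 ends trial treatment at a primary outcome, which in three cohorts can be non-fatal, while sections 5.8 and 6.3 say participants should normally continue

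*Protocol*

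**What the plan says.** Section 5.2 states how long randomised tablets are taken: "This should be continued for at least five years or until one of the primary outcome measures is met". It points to section 10.2 for the outcomes. Table 7 there gives the cohort-specific primary outcomes:

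- **Breast:** invasive recurrence, contralateral invasive cancer, a further item listed as "Second primary (non-breast) invasive cancer", or death.
- **Colorectal:** local or distant recurrence, or death.
- **Prostate:** PSA failure, clinical progression, start of salvage treatment, or prostate cancer death.
- **Gastro-oesophageal:** death only.

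Section 5.8 covers treatment after recurrence in the randomised phase: "participants should normally continue to take their allocated trial treatment". It allows exceptions, introduced by "Where the Investigator feels that this is not appropriate". Section 6.3 agrees: "Following disease recurrence/progression in the randomisation phase, participants should normally continue to take their trial medication".

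Section 5.7 says "an individual participant may stop treatment early for any of the following reasons". Its list contains neither recurrence nor a primary outcome event. The trial summary describes the tablets as "to be taken daily for at least five years", with no stop at an event. Appendix XIV, section 6A, defers to 5.8 for POLEM participants: "Participants on the Add-Aspirin trial can continue trial medication upon recurrence".

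**The concern.** For a participant with a non-fatal primary event, section 5.2 ends treatment and sections 5.8 and 6.3 normally continue it. Nothing in the protocol says which section prevails. Section 5.2 carries the heading on randomised treatment and is where a site would look for duration, so some sites could withdraw tablets at the event while others continue.

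The analysis exposed to this is combined overall survival, a co-primary outcome. Sections 10.3.2 and 10.4.5 expect its effect to appear only from about three years or later. Table 9 gives detectable hazard ratios of 0.92 to 0.93, so there is little room for dilution. Tablets withdrawn at an earlier recurrence would be withdrawn before part of the period in which benefit is expected.

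**Working it through.** **Step 1: do the sections conflict?** The claim is textual, and the protocol states no figure to reproduce.

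| Place | After a non-fatal primary event |
|---|---|
| 5.2 | Treatment ends |
| 5.7 | Not listed as a reason to stop |
| 5.8 | Normally continue; investigator may decide otherwise |
| 6.3 | Normally continue; refers to 5.8 |
| Summary | At least five years, no event stop |
| Appendix XIV, 6A | May continue, by reference to 5.8 |

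The outcomes meant in 5.2 cannot be read as death alone. It cites section 10.2, and sections 6.3 and 6.3.1 themselves call biochemical failure a primary outcome event. Every other place favours continuing, so 5.2 is the text in error. The amendment log (section 16.1.2, item 18) records that recurrence was removed from 5.7 as a reason to discontinue. That is evidence of intent only.

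**Step 2: who could meet the conflict?** This is a rough bracket over five years, not a measure of harm.

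Inputs from sections 10.4.1, 10.4.2, 10.4.4 and 10.4.5:
- Participants: 3,100 breast, 2,600 colorectal, 2,120 prostate; 7,820 in all.
- One third placebo, two thirds aspirin: 1,033/2,067, 867/1,733 and 707/1,413. Aspirin total 5,213.
- Five-year primary event rates, placebo then aspirin at the target effect: breast 20% and 16%, colorectal 30% and 25%, prostate (combined cohort) 31% and 25%.
- Five-year control-group mortality: breast 10%, colorectal 20%.

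*Upper figure: all primary events, including deaths as first events.*
- Placebo: 0.20 × 1,033 + 0.30 × 867 + 0.31 × 707 = 207 + 260 + 219 = 686.
- Aspirin: 0.16 × 2,067 + 0.25 × 1,733 + 0.25 × 1,413 = 331 + 433 + 353 = 1,117 (21.4% of 5,213).
- Total: 1,803 of 7,820 (23.1%).

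Using the separately powered prostate groups instead, prostate events are 920 × (0.25/3 + 0.17 × 2/3) + 1,200 × (0.35/3 + 0.27 × 2/3) = 181 + 356 = 537 rather than 572. The total is then about 1,770.

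*Lower figure: every five-year death in breast and colorectal is assumed to be a first event, at the same rate in both arms.* Prostate is left unreduced, because its outcome counts only prostate cancer deaths.
- Placebo: 0.10 × 1,033 + 0.10 × 867 + 219 = 103 + 87 + 219 = 409.
- Aspirin: 0.06 × 2,067 + 0.05 × 1,733 + 353 = 124 + 87 + 353 = 564 (10.8% of 5,213).
- Total: 973 of 7,820 (12.4%).

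Actual aspirin exposure could differ only in the aspirin arms, so the relevant counts are about 564 to 1,117. Neither end is reduced for participants already off tablets, for stops that 5.8 allows, or for incomplete follow-up.

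**Step 3: which overall-survival events could be affected?** Only deaths that follow a non-fatal primary event occurring on treatment. The protocol does not give that share. Section 10.4.5 expects about half of the combined deaths in the gastro-oesophageal cohort, where the clause has no effect. Section 10.2 expects many deaths in the other cohorts to be from causes other than cancer. Under the assumption behind the lower figure, no breast or colorectal death within five years follows a recurrence, so dilution there over that period would be nil.

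**The case against.** The strongest reply is that the protocol largely resolves the matter itself. Section 5.8 is the section dedicated to treatment after recurrence, 6.3 repeats its rule, Appendix XIV defers to it, and 5.7 lists no event stop. A site stopping tablets on 5.2 alone would have to disregard two explicit instructions, and nothing in the protocol shows that any site has. This stands as a reason to keep the point modest. It does not make 5.2 correct.

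Section 5.2 might also be read as a minimum period, since it says at least five years and gives no express order to withdraw tablets. A reader should not infer that it permits treatment only until an outcome; it does not say only. But the minimum-period reading is strained, because the second half of the sentence names an alternative end point.

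The word normally in 5.8 and 6.3 does not reconcile the texts either. Exceptions there rest on the investigator's judgement, whereas 5.2 is triggered by the event itself.

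PSA failure is already largely covered. Section 6.3 counts PSA among the means of assessing recurrence and progression, names biochemical failure as a primary outcome event, and then gives the continue rule. The clear gap is breast second primary cancers.

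**Conclusion.** The contradiction is real, and the clause in 5.2 is wrong as written for the breast, colorectal and prostate cohorts. It is an internal inconsistency; the design choice to continue by default is clear and is not criticised. It should be corrected, because it concerns when to stop the investigational product.

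Two stronger readings are not supported:

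- A reader might infer that the primary analyses are compromised. They are not: section 10.8.1 analyses by allocation, and the disputed exposure follows the event that each cohort-specific outcome counts.
- A reader might take 970 to 1,800 participants as the size of the harm. It is only a bracket of who could meet the conflict, resting on planning rates and target effects, and its upper end includes deaths, after which no exposure is in dispute.

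The supported consequence is possibly inconsistent exposure after an event and some dilution of the combined overall-survival effect. Its size cannot be computed from the protocol. It is limited by the gastro-oesophageal share of deaths, by non-cancer deaths elsewhere, and by the discretionary stops in 5.8.

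**What to change.** In section 5.2, delete the alternative end point (the clause beginning with or until) and cross-refer to sections 5.7 and 5.8. In section 5.8, state that the continue-by-default rule, with the existing investigator discretion, applies to any non-fatal primary outcome event, including breast second primary cancers. Notify sites.

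The cost is one clause removed, one sentence added and a note to sites. No new data collection and no change to sample size or analysis is needed.
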